5. SAMPLE SIZE CALCULATION

Table 2 provides the summary statistics for the corresponding efficacy endpoints based on change in the average pain score for the low dose and placebo groups from the intent-to-treat population and efficacy groups in the Phase II study (Protocol VMDN-002, injections at Day 0 and Day 14 only).

	ľ	T	EFFICACY				
	VM202	PLACEBO	VM202	Placebo			
		Mean ((SD)				
Month 3	-2.89 (2.47)	-1.70 (1.72)	-3.03 (2.53)	-1.53 (1.76)			
Month 6	-2.58 (2.18)	-1.63 (1.75)	-2.78 (2.23)	-1.59 (1.89)			
	Percentage of Subjects with $a \ge 50\%$ Reduction						
Month 3	45.9%	23.8%	48.4%	17.6%			
Month 6	34.3%	15.0%	38.7%	17.6%			

TABLE 2. Mean and Standard Deviation of Pain Score Changes fromBaseline and the Percentage of Subjects with at Least a 50% Reduction;Low Dose versus Placebo Group in Phase II Study

The sample size for the primary efficacy endpoints was calculated based on the following assumptions:

- Based on the Phase II findings, it is assumed that the standard deviation of the pain score change from baseline will be 3.0. The true percentage of subjects with a pain reduction of ≥ 50% is assumed to be 35% and 18% for the VM202 group and placebo group, respectively.
- The statistical power is 90% for a detectable mean difference of -1.0 (i.e., mean pain reduction for the VM202 group is higher than that for the Placebo group) for Statistical Hypotheses (I) in Section 4.1 using a t-test. The statistical power is also 90% for Statistical Hypotheses (II) in Section 4.1 provided the assumptions of $p_t = 35\%$ and $p_c = 18\%$ using a chi-square test.
- The two-sided significance level is 0.05. Since a formal statistical conclusion for the second primary efficacy endpoint will not be made unless the null hypothesis of the first primary efficacy endpoint is rejected, no adjustment on the significance level is performed.
- The randomization ratio for the VM202 group and the placebo group is 2:1.

Based on the assumptions above, the sample sizes calculated for the VM202 group and placebo group are 286 and 143 subjects, respectively, for Statistical Hypotheses (I); those for Statistical Hypotheses (II) are 212 VM202 subjects and 106 placebo subjects.

Therefore, 286 VM202 subjects and 143 placebo subjects are needed with data at the 3-month follow-up for the primary data analyses. With a dropout rate of 10%, at least 477 subjects should be randomized in order to have 318 VM202 subjects and 159 placebo subjects.

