7.7. Missing Average 24-hour Pain Scores at 3, 6, or 9 Months

The Daily Pain and Sleep Interference Diary is to be completed within 14 days of the 3-, 6- and 9-month visits. The average 24-hour pain score for a visit will be considered as missing if fewer than 5 of 7 days of Daily Pain and Sleep Interference Diary entries are provided. Sensitivity analyses for the mean change in the average 24-hour pain score will include the following imputation approaches for missing values at 3-months, 6-months, or 9-months. It is important to note that over-stratification may result when the total list of pre-specified factors are considered. Under this scenario, the least represented factor will be removed and the imputation will be re-run. This process will be followed until the imputed dataset is complete.

- Multiple imputation: Each missing pain score will be imputed ten times to generate ten imputed complete data sets based on the Markov Chain Monte Carlo (MCMC) method with baseline pain score, 3-month, 6-month, 9 month pain score, and categorical covariates of baseline use of gabapentin and/or pregabalin, baseline HbA1c, gender, and age. The imputed score will be rounded to the first decimal point. The results of the ten tests from the continuous Repeated Measures Model (Section 8.4.2) using these data will be combined.
- Mean of the other group $(MOTH)^3$ as follows:
 - 1. For a subject with a missing 3-month, 6-month, or 9-month average 24-hour pain score, identify the subject's following baseline characteristics:
 - Study treatment group
 - Baseline use of gabapentin and/or pregabalin.

³ Unnebrink K and Windeler J, "Intention-to-treat methods for dealing with missing values in clinical trials of progressive deteriorating diseases," Statistics in Medicine, 2001;20: 3931-3946.

- Baseline average 24-hour pain score (< median or \geq median)
- HbA1c (< median or \geq median)
- Gender (male or female)
- Age (<65 years and \geq 65 years).
- 2. The missing 3-month, 6-month, or 9-month average 24-hour pain score will be imputed by using the mean average 24-hour pain score obtained at the same time point of those subjects in the other treatment group who match the subject's baseline characteristics. For example, for the missing pain scores of the VM202 subjects, the mean pain scores of the placebo subjects within the same covariate groups will be used to impute the missing pain scores.

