- 3. The baseline characteristics will be re-examined for appropriateness and may be re-categorized (due to small sample size) before unblinding the study.
- 4. The imputed score will be rounded to the first decimal point. The imputed scores will be included in the continuous Repeated Measures Model (Section 8.4.2) analysis.

Sensitivity analyses for the percentage of subjects with a reduction in the average 24-hour pain score of at least 50% will include the following imputation approaches for missing values at 3, 6, or 9 months.

- Imputed average 24-hour pain scores at 3, 6, or 9 months from the multiplyimputed pain score datasets described above. The results of the ten tests from the categorical Repeated Measures Model (Section 8.4.2) will be combined.
- Missing pain score will be imputed from the MOTH-imputed dataset described above and the categorical Repeated Measures Model (Section 8.4.2) will be used for the data analyses.
- Multiple imputation for the missing responder outcomes, 1 (Yes) or 0 (No), by fully conditional specification logistic regression method: each missing responder outcome will be imputed ten times to generate ten imputed complete data sets using a logistic regression model with baseline use of gabapentin and/or pregabalin, and categorical baseline HbA1c, gender, and age as covariates. The results of the ten tests from the categorical Repeated Measures Model (Section 8.4.2) will be combined.

Steps to generate the MMRM analysis are presented below; different options will be used depending on the exact model being run:

Run PROC MI using output dataset ("outmi") containing the original and imputed values, add "by imputation" to the SAS code and "solution" as an option on the MIXED model statement. The resulting file is available via ODS output: solutionf=mixparms;"

Run the following PROC MIANALYZE code: PROC MIANALYZE parms(classfull)=mixparms; class trtp avisitn basemed; modeleffects intercept trtp avisitn trtp*avisitn basemed; run;

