The model will include treatment, visit, treatment-by-visit interaction, baseline use of gabapentin and/or pregabalin, and baseline average 24-hour pain scores as covariate with an unstructured variance-covariance matrix. The point estimates for the least-squares mean of the treatment difference (VM202 – Placebo) at 3 months and the corresponding 95% confidence interval and p-value will be summarized.

The SAS code to be used to conduct the analysis is presented below:

PROC GLIMMIX DATA=work method=quad(Qpoint=); class usubjid trtp avisitn basemed;
MODEL critvar(event='Y') = trtp base avisitn basemed trtp*avisitn / DIST=binary
LINK=LOGIT SOLUTION;
random INTERCEPT / SUBJECT=usubjid type=un;
lsmeans trtp *avisitn / diff cl;
RUN;

Where USUBJID: subject ID
TRTP: treatment
AVISITN: variable representing visits (Primary model will include the 3, 6, and 9 month visits)
CHG: change in average pain score from baseline
BASE: baseline average pain score
BASEMED: a Y/N variable indicating if the subject took gabapentin/pregabalin at baseline.
CRITVAR: a Y/N variable indicating if the subject had at least a 50% reduction in baseline pain score from baseline at that visit
Qpoint: Number of quadrature nodes to clarify the dimensionality

Other variance-covariance structures selected from among compound symmetry, Toeplitz, and autoregressive (1) options will be substituted based on the lowest AIC if convergence problems arise.

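### The covariate list for the responder multiple imputation in SAP 7.7 leaves out treatment, baseline pain and the subject's other visits, so this sensitivity analysis shrinks the Month 3 subject-specific log-odds ratio

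*SAP*

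**What the plan says.** SAP 7.7 gives three imputation approaches as sensitivity analyses for the responder endpoint. The third is described as "Multiple imputation for the missing responder outcomes, 1 (Yes) or 0 (No), by fully conditional specification logistic regression method", and "each missing responder outcome will be imputed ten times to generate ten imputed complete data sets". Its model is specified "using a logistic regression model with baseline use of gabapentin and/or pregabalin, and categorical baseline HbA1c, gender, and age as covariates". These are four baseline variables and nothing else.

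The pain-score imputation by MCMC in the same section has a fuller list: "with baseline pain score, 3-month, 6-month, 9 month pain score, and categorical covariates of baseline use of gabapentin and/or pregabalin", followed by HbA1c, gender and age. It names baseline pain and all three visits, though not treatment.

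The completed responder data go to the categorical model of SAP 8.4.2. Its code reads "MODEL critvar(event='Y') = trtp base avisitn basemed trtp*avisitn" for the fixed effects and "random INTERCEPT / SUBJECT=usubjid type=un" for the within-subject correlation. The reported treatment effect is therefore a log-odds ratio conditional on the subject.

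**The concern.** An imputation model should carry at least the terms that the analysis model uses. Here it lacks three of them.

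- **Treatment and treatment-by-visit.** Without them, missing responses in both arms are drawn at one common rate, which pulls the arms together.
- **Baseline pain.** It is in the analysis model and in the MCMC list.
- **Responses at the other visits.** Without them, a subject observed as a non-responder at Month 3 who then leaves is imputed at Month 6 as if that were unknown. For a subject who leaves before Month 3, the three visits are imputed independently of one another. Both weaken the correlation that the random intercept estimates, and the subject-specific coefficient shrinks with it.

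At stake is how this check on the second primary endpoint is read. A smaller estimate could be taken as fragility to missing data when it comes from the imputation model.

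**Working it through.** **1. The plan's own figures.** The documents give no figure for imputation bias. The planning rates (SAP 5) do reproduce. With 35% vs 18%, 2:1 allocation and pooled rate (2 × 35% + 18%)/3 = 29.33%, the placebo size is [1.960 × √(1.5 × 0.2933 × 0.7067) + 1.282 × √(0.18 × 0.82 + 0.35 × 0.65/2)]² / 0.17² = (1.093 + 0.655)²/0.0289 ≈ 105.7, so 106 placebo and 212 VM202, as stated. For the first endpoint, 286 + 143 = 429, and 429/0.90 = 476.7, so 477 randomised, as stated.

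**2. Omitting treatment, closed form.** Take the planned 10% dropout as the share missing at Month 3, unrelated to response, and the four listed covariates as unrelated to response. Both arms are then imputed at 29.33%.

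- VM202: 0.9 × 35% + 0.1 × 29.33% = 34.43%
- Placebo: 0.9 × 18% + 0.1 × 29.33% = 19.13%
- True marginal log-odds ratio: ln(0.35/0.65) − ln(0.18/0.82) = 0.897
- After imputation: ln(0.3443/0.6557) − ln(0.1913/0.8087) = 0.797
- Shrinkage: 1 − 0.797/0.897 = 11.1% (5.6% at 5% missing, 16.6% at 15%)

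**3. The SAP 8.4.2 model, by simulation.** 15,000 subjects, rates 35%/18% at each visit, random-intercept logistic model fitted by quadrature. Assumed, because the documents do not say: random-intercept SD 1, 2 or 3; baseline pain effect −0.3 log-odds per SD; listed covariates unrelated to response; about 10% missing. Simulation noise is about 2 to 3 points. Entries are the percentage shrinkage of the Month 3 subject-specific log-odds ratio against complete data.

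| Missing data | Imputation model | SD 1 | SD 2 | SD 3 |
|---|---|---|---|---|
| Left before Month 3 | As listed | 11.7 | 15.8 | 19.6 |
| | + treatment | 0.9 | 5.0 | 8.8 |
| | + baseline pain, visits | 9.0 | 9.2 | 9.0 |
| | + all three | −0.9 | 0.5 | −0.1 |
| Intermittent | As listed | 14.3 | 20.3 | 27.7 |
| | + treatment | 3.1 | 9.8 | 17.8 |
| | + baseline pain, visits | 6.9 | 3.7 | 4.5 |
| | + all three | −1.7 | −2.1 | −0.4 |
| Month 3 only | As listed | 14.4 | 17.5 | 18.9 |
| | + treatment | 2.8 | 5.5 | 7.8 |
| | + baseline pain, visits | 10.0 | 6.7 | 4.2 |
| | + all three | 2.8 | 1.7 | 1.6 |
| Months 6/9 only | As listed | 1.2 | 4.9 | 9.7 |
| | + treatment | 1.3 | 4.2 | 8.9 |
| | + baseline pain, visits | −0.7 | 0.1 | 0.4 |
| | + all three | −0.2 | 0.0 | 0.6 |

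Where Month 3 data are missing, the marginal log-odds ratio shrinks by about 10 to 14% as listed, and by −1% to +2% once treatment is in.

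**4. Correlated pain changes instead of a random intercept.** Assumed: between-visit correlation 0.5 to 0.7, change SD 2.4 to 3.0, response about 33% vs 20%, about 9% missing at Month 3, and more later losses among Month 3 non-responders than responders. With treatment added but baseline pain and visits left out, the Month 3 subject-specific log-odds ratio shrinks by roughly 6 to 17%. At correlation 0.7 the random-intercept SD falls from 2.6–2.7 to 2.1–2.2. With the list exactly as written the shrinkage is roughly 17 to 25%. With all three added the estimate returns to within about 5% of complete data. In one run where the Month 3 gaps were dropouts, it fell from 1.36 to 1.13 with treatment only (1 − 1.13/1.36 = 17%) and returned to 1.33 with all three (1 − 1.33/1.36 = 2%).

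**The case against.** The strongest reply is that fully conditional specification means imputing each incomplete variable from the others. The visits may therefore already be in the chain, with the four named variables as additional covariates. That reading is possible, and the SAP does not exclude it. But the sentence sets out a model with a closed list, and the MCMC bullet names the visits where it wants them. Nor would chaining the visits bring in treatment or baseline pain.

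Second, with treatment in the model most of what remains is a change of scale. The marginal log-odds ratio is nearly unbiased and the standard error falls with the coefficient. In runs with treatment included, the z-statistic averaged about 97% of the observed-data value (range 88 to 103%). This stands, and it limits the harm. It does not cover the list as written, where treatment is absent and the marginal contrast shrinks too. The estimate that SAP 8.4.2 reports is also the subject-specific one.

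Third, a subject who leaves before Month 3 has no later diary to borrow from. That is true of observed data. Conditioning on the other visits still restores the correlation among that subject's imputed values.

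Fourth, another responder bullet derives status from the MCMC-imputed scores, which use baseline pain and every visit. That is a partial safeguard only, since the MCMC list does not name treatment either.

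**Conclusion.** The point holds as a specification gap in one of three responder imputation analyses. The listed model lacks treatment, baseline pain and the other visits, and all three are needed. Adding baseline pain and visits without treatment still leaves about 4 to 10% shrinkage when Month 3 data are missing. Adding treatment alone leaves roughly 6 to 17% under the step 4 assumptions (1 to 18% in the step 3 table). All three together remove it to within simulation noise in step 3.

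A reader might infer more than the documents support:

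- **A single figure for the shrinkage.** The documents fix only the planning rates and a 10% dropout. Correlation, missingness pattern and random-intercept variance are assumptions, so only a range is defensible.
- **That the SAP definitely ignores the other visits.** It does so as listed, but the method's name leaves room for the other reading.
- **That the second primary endpoint or the testing hierarchy is biased.** Neither depends on this imputation. The error is toward no effect and confined to a robustness check.

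The correction is worth making before unblinding. It does not threaten the trial's main conclusion.

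**What to change.** In the third responder bullet of SAP 7.7, state that the FCS logistic model for each visit includes, besides the four listed covariates:

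1. randomised treatment, or that imputation is run separately by arm;
2. baseline average 24-hour pain score, as a continuous variable;
3. responder status (or pain score) at the other two of Months 3, 6 and 9.

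All of these are already collected. The cost is one sentence of SAP text, a matching change in code and a slightly larger imputation model.

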7.7.1. Missing Values for BPI-DPN and MNSI

No imputation for missing individual item scores within the BPI-DPN (both pain severity and interference) and MNSI (both physical assessment and history) questionnaire will be performed. Missing individual item scores of the BPI-DPN may be imputed for the calculation of the average score within a domain using the average score across the nonmissing items within the domain at a subject's visit provided that the proportion of missing items scores within that domain is less than 25%; otherwise the domain score at that visit is missing. A similar method will be used when deriving total MNSI scores using a 'worst case' imputation approach. Missing individual items will be imputed as the category corresponding to the largest number of points in the total score calculation. This equates to a response of 'Yes' to questions 1-3, 5-6, 8-9, 11-12, and 14-15 and 'No' to questions 7 and 13 on the history assessment. On the physical assessment it equates to a response of 'No' on the 'Appearance of Feet' question, a response of 'Present' on the 'Ulceration' question, and a response of 'Absent' on the 'Ankle Reflexes', 'Vibration perception at great toe', and 'Monofilament' questions.

7.7.2. Missing Dates

If a start or stop date for an adverse event or a concomitant medication use is completely missing, it will not be imputed. If it is partially missing, imputed dates specified in Table 4 will be used to derive the duration of the adverse event or the duration of the medication use. Missing years will not be estimated under any conditions. Missing dates of medical history will not be imputed.

TABLE 4. Imputation Rules for Partial Adverse Event or Concomitant Medication Start and Stop Dates

	MISSING	IMPUTATION	EXCEPTION
Start Date	Day	01	Default to Study Day 0 (day of first injection procedure) if an event starts in the same year and month as Study Day 0
	Day/Month	01JAN	Default to Study Day 0 if an event starts in the same year as Day 0

Stop Date	Day	-	Default to the End of Study Date if the imputed event stop date is after the End of
	Day/Month	31DEC	Study Date or before start day of the event

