3.7. PRIOR AND CONCOMITANT MEDICATION

All concomitant medications (taken within 60 days of the first injection) will be recorded at each study visit. For each medication taken, the following information will be collected:

- Medication trade name;
- Indication for which the medication was given;
- Dose/strength, route, and frequency of administration;
- Date started and date stopped (or continuation at study exit).

EXAMINATIONS AND EVALUATIONS 4.

4.1. **EVALUATIONS CONDUCTED AT BASELINE ONLY**

MEDICAL HISTORY 4.1.1.

A complete medical history will be obtained at Baseline. All positive and negative findings will be carefully documented on the study worksheets. Any new finding discovered during the Screening/Baseline evaluation and prior to the first study drug administration (Day 0) will be considered to be part of the medical history and will not be recorded as an adverse event.

The Investigator will perform an especially detailed assessment of past diabetes history to include all events and interventions prior to study enrollment. Other potential causes of peripheral neuropathy will be excluded (e.g., alcohol consumption, renal failure, liver disease, hypothyroidism, collagen vascular diseases, vasculitis, osteoarthritis of the ankle or foot, gout, bursitis, fasciitis, and B-12 or folate deficiency).

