6.4 Per Protocol (PP) Populations

Three PP populations are defined. All PP population should be absent of any major protocol deviations.

The Per Protocol Medication population is a subset of the mITT and corresponds to the mITT population defined in protocol version H. It includes all mITT subjects who meet the following criterion:

• Have not used the protocol specified prohibited concomitant medications, such as COX-2 inhibitor drug(s) or non-specific COX-1/COX-2 inhibiting drugs which may interfere with VM202 or pain medication usage which may intensify the effect of VM202/placebo on pain, for more than 14 cumulative days during the entire study. The use and effect of protocol specified prohibited concomitant medications will be determined by the Clinical Data Review Committee (CDRC) in a blinded fashion prior to analyses.

The Per Protocol Dosing population is a further subset of the mITT and corresponds to the PP population defined in protocol version H. It includes all mITT subjects who meet the following criterion:

- Subject received all injections based on the randomized treatments.
- Additional criteria, if any, established before unblinding the randomization code by the CDRC that is masked to the treatment information of each study subject.

The Per Protocol Diary population is a subset of the mITT and includes all mITT subjects whose Daily Pain and Sleep Interference Diary at the 3-month follow-up is completed for a minimum of 5 of 7 days within 14 days prior to the Day 90 visit.

All three PP populations will be used in the sensitivity analyses for the primary efficacy endpoints. The PP Medication and PP Dosing populations will also be used in sensitivity analyses of the secondary efficacy endpoints.

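### SAP Table 4 applies an adverse-event partial-date rule to medications with no check for a recorded stop before Day 0, so some washed-out drugs can acquire months of false on-study use

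*SAP*

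**What the plan says.** SAP 7.7.2 sets one rule for adverse events and concomitant medications. Completely missing dates are left alone: "If a start or stop date for an adverse event or a concomitant medication use is completely missing, it will not be imputed". Partial dates are filled from Table 4, and the imputed dates "will be used to derive the duration of the adverse event or the duration of the medication use".

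The Table 4 rules are:

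- **Start, day missing:** the first of the month, except "Default to Study Day 0 (day of first injection procedure) if an event starts in the same year and month as Study Day 0".
- **Start, day and month missing:** 1 January, except "Default to Study Day 0 if an event starts in the same year as Day 0".
- **Stop, day and month missing:** 31 December. The base rule for a stop with only the day missing is not legible in the text available.
- **Stop, exception:** "Default to the End of Study Date if the imputed event stop date is after the End of", continuing "Study Date or before start day of the event".

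Two other places bear on this. SAP 6.4 bars from the PP Medication population any subject who used prohibited medication "for more than 14 cumulative days during the entire study", with use and effect determined by the blinded Clinical Data Review Committee (CDRC). Protocol 3.7 defines what is logged: "All concomitant medications (taken within 60 days of the first injection) will be recorded at each study visit".

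**The concern.** The Day 0 default suits adverse events, because these are collected only from the first injection (Protocol 5.3, SAP 8.5.3) and cannot truly start before it. Medications can. The protocol admits subjects who wash out prohibited drugs before the baseline diary, so drugs that stopped shortly before Day 0 are expected in the log.

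For such a drug, a partial start in the Day 0 year is pushed forward to Day 0. A partial stop that correctly lies before Day 0 then looks impossible, and the exception resolves the conflict by moving the stop to End of Study. The rule thereby discards the one piece of information that shows the drug had ended.

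At stake is a subject's place in the PP Medication population. Possibly also at stake are the pain scores removed in the second observed-case sensitivity set of SAP 8.4.4, which excludes scores influenced by prohibited drugs as described in 6.4.

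**Working it through.** The plan gives no figure on this point to reproduce, so the check applies Table 4 literally to drugs that truly stopped before Day 0 (true on-study use 0 days).

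**Inputs**

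- Table 4 start and stop rules, as above.
- Stop with the day missing: assumed to be the last day of the month. If the stop month ends before Day 0, any imputed day in that month gives the same outcome.
- End of Study: assumed to be the Day 270 visit. Its ±14-day window gives Day 256 to Day 284.
- Day 0: assumed to be 15 June 2017, so Day 270 is 12 March 2018.
- Threshold: more than 14 cumulative days (SAP 6.4).

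**Formula**

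On-study days = min(stop, End of Study) − max(start, Day 0) + 1, set to 0 if negative.

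**Worked cases**

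| Recorded start | Recorded stop | Imputed start | Imputed stop | On-study days |
|---|---|---|---|---|
| 2017 | May 2017 | 15 Jun 2017 | 31 May, before start, so 12 Mar 2018 | 271 |
| 2017 | 2017 | 15 Jun 2017 | 31 Dec 2017 | 200 |
| 2015 | 2017 | 1 Jan 2015 | 31 Dec 2017 | 200 |
| 2017 | 20 May 2017 | 15 Jun 2017 | 20 May 2017 (not imputed) | 0; stop precedes start |
| 2015 | May 2017 | 1 Jan 2015 | 31 May 2017 | 0 |
| Apr 2017 | May 2017 | 1 Apr 2017 | 31 May 2017 | 0 |

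Row 1: Day 0 to Day 270 inclusive is 270 + 1 = 271 days. Over the visit window it is 256 + 1 = 257 to 284 + 1 = 285.

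Rows 2 and 3: 15 June to 31 December is 16 + 31 + 31 + 30 + 31 + 30 + 31 = 200 days. The result is the same with a 2015 start, so the 31 December stop rule causes it, not the Day 0 default.

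**How far this depends on the chosen date**

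The same rules were run for every Day 0 in 2017 and for true stops 14 to 60 days before it (365 × 47 = 17,155 combinations per date pattern). Drugs were taken as started either 30 days or two years before the stop. The lower limit of 14 days reflects the Appendix 3 washout for opioids and other therapies: seven days before a seven-day diary.

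| Date pattern | More than 14 days | 60 days or more | Maximum |
|---|---|---|---|
| Complete stop, any start | 0% | 0% | 0 |
| Month-year stop, complete or month-year start | 0.3% | 0% | 17 |
| Month-year stop, year-only start, drug begun two years before | 0.3% | 0% | 17 |
| Month-year stop, year-only start, drug begun 30 days before | 72.8% | 72.5% | 271 |
| Year-only stop, any start | 86.0% | 73.7% | 271 |

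These are shares of hypothetical date combinations, not of subjects.

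**Effect of a guard**

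Suppose a drug is treated as prior when the latest date compatible with its recorded stop is before Day 0. The first worked case then falls from 271 to 0 days, and the 72.8% row falls to 0.3% (maximum 17 days). The year-only-stop row stays at 86.0%, so it needs its own rule.

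**The case against.** The strongest reply is that Table 4 does not reach these drugs. It speaks of concomitant medication, and SAP 8.5.6 defines that as use after the first dose, with prior medication separate. For a missing start date, 8.5.6 calls a drug concomitant only if its stop is missing or on or after treatment start. A drug recorded as stopped in May, with Day 0 in June, would be prior. This has force, but it does not settle the matter. Protocol 3.7 uses concomitant for drugs taken within 60 days of the first injection, 8.5.6 has no classification rule for partial dates, and a stop known only to the Day 0 year cannot be classified without imputing it.

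A second reply is that the CDRC decides prohibited use, blinded, and that SAP section 7 sends questionable values to it, alongside the site queries and computerised checks in Protocol section 14. That is a real safeguard, and an absurd interval might well be caught. But the SAP does not say whether the 14-day count uses imputed dates. Equally, nothing says that the committee works from Table 4 durations, so it cannot be asserted that compliant subjects will be dropped.

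A reader might also infer that the rule generally turns washed-out drugs into months of prohibited use, or that it distorts the medication tables. The documents do not support either. The Day 0 default moves only starts whose known part matches the Day 0 year, or month and year. Months of false use also require a partial stop. The summaries in 8.5.6 are counts and percentages of users, so duration does not enter them. Nor is every washed-out drug necessarily logged: Protocol 3.7 covers 60 days, whereas screening may span 90.

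**Conclusion.** The defect is real but narrow. Read literally, Table 4 gives a wrong answer in two situations:

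1. **Year-only start in the Day 0 year with a month-year stop before Day 0:** about 271 days of false on-study use (257 to 285 over the visit window).
2. **Year-only stop in the Day 0 year, whatever the start:** 200 days for a 15 June Day 0, through the 31 December rule.

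A complete stop before Day 0 can leave an impossible interval but adds no on-study days.

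The consequence is confined to the PP Medication population and possibly the sensitivity set that excludes affected scores. The primary and key secondary analyses use the ITT population without a prohibited-medication exclusion and are unaffected. The documents do not say how often partial dates of these kinds occur, so no count of affected subjects can be given. The figures rest on the assumed Day 0 and on End of Study being the Day 270 visit; the spread in the second table also rests on month-end imputation of day-missing stops.

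**What to change.** Revise Table 4 before unblinding:

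- Restrict the Day 0 start default to adverse events. Impute partial medication starts to the first of the month or 1 January.
- For medications, delete the rule that sends a stop before the start to End of Study. With starts imputed early and stops late, such an inversion would signal a recording error and should be queried.
- Treat any drug whose latest possible recorded stop is before Day 0 as prior, and align SAP 8.5.6 with Protocol 3.7 on what concomitant means.
- For stops known only to the Day 0 year, query the site, or cap the stop at the day before Day 0 when the Day 0 medication review shows that the drug had ended.
- State in SAP 6.4 whether the CDRC's 14-day count uses imputed dates.

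In the worked cases, the first three changes take 271 days to 0, and the cap takes 200 days to 0 where the Day 0 review supports it. The cost is one SAP table, short clarifications in SAP 6.4 and 8.5.6, minor programming, and site queries for whichever records have year-only stops.
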